9.2. Morning Window Summaries

The peak morning period for ACTH, 17-OHP, androstenedione, and testosterone levels is between 0700 and 1000 hours. For the purposes of analysis, this timeframe will be referred to as the "morning window" and includes all PD biomarker measurements (excluding cortisol) taken during this time. Specifically, the morning window timepoints for PD draws are 12- and 15-hours post-evening crinecerfont dose. This group of timepoints will be summarized using the average of the two morning window timepoints at each visit. If only one timepoint is available, this value will be used as the morning window value. If both timepoints are missing, the morning window value for that subject/visit will be reported as missing.

The morning window values will be summarized with descriptive statistics by PD parameter and visit. In addition to the observed values, descriptive statistics will also be generated for the change from PD baseline to Day 1 and from PD baseline to Day 14, as well as the percent change from PD baseline to Day 1 and from PD baseline to Day 14. Percent change from PD baseline to Day 1 and Day 14 for each subject will be presented as waterfall plots by PD parameter.

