12.7. Pharmacodynamic Data

Morning 17-OHP (serum; ng/dL) from the 8- and 12-hour postdose samples (collected at 0300 and 0700 hours).

17-OHP at all other times, androstenedione (serum; ng/dL), testosterone (serum; ng/dL), cortisol (serum; μ g/dL), and adrenocorticotropic hormone (ACTH; plasma; pg/mL). Summaries of PD measures will include both observed values and changes from timepoint-matched PD baseline values.

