6.4.2. Change and Percent Change from Baseline

Change from baseline is calculated as (postbaseline value – baseline value).

Percent change from baseline is calculated as (change from baseline/baseline value * 100).

If either the baseline or postbaseline value is missing, the change from baseline and percent change from baseline will also be missing. The percent change from baseline will also be missing if the baseline value is equal to zero.

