9.3. Responder Summaries

The PD biomarker data will also be summarized based on responder definitions for ACTH, 17-OHP, androstenedione, and testosterone (female subjects only). The first responder definition will be composed of subjects who have a 50% or greater reduction from PD baseline to Day 14 in the average of their morning window values. The second responder definition will be composed of subjects who have a 50% or greater reduction from PD baseline to Day 14 for at least one timepoint in the morning window period. The frequency and percentage of subjects meeting each of these responder definitions will be summarized by parameter.

Additionally, a responder definition for the ratio of androstenedione to testosterone (A4/T) in male subjects will be composed of male subjects who have an A4/T ratio greater than or equal to 0.5 (based on the average of the morning window values for androstenedione and testosterone) at PD baseline and who achieve an A4/T ratio less than 0.5 (based on the average of the morning

Neurocrine Biosciences, Inc. Statistical Analysis Plan

window values for androstenedione and testosterone) at Day 14. The frequency and percentage of male subjects meeting this responder definition will be summarized.

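### When one morning PD sample is missing at only one visit, SAP 9.2 compares a 0700/1000 h mean with a single clock time

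*SAP*

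**What the plan says.** SAP 9.2 fixes the window: "Specifically, the morning window timepoints for PD draws are 12- and 15-hours post-evening crinecerfont dose", that is, 0700 h and 1000 h. The summary rule is "This group of timepoints will be summarized using the average of the two morning window timepoints at each visit", and the exception is "If only one timepoint is available, this value will be used as the morning window value". Window changes and percent changes are planned from PD baseline to Day 1 and to Day 14. In the SAP's labelling each of these means the whole 24-hour series that starts that evening.

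The window values also feed three later outputs:
- SAP 9.3, first responder definition: "50% or greater reduction from PD baseline to Day 14 in the average of their morning window values".
- SAP 9.3, male A4/T responder: the ratio of the two window values at each visit, judged against 0.5.
- SAP 9.4: scatter plots of window percent change against exposure for ACTH, 17-OHP and androstenedione.

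The second responder definition in SAP 9.3 works by timepoint: "50% or greater reduction from PD baseline to Day 14 for at least one timepoint in the morning window period".

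On change in general, Protocol 12.7 says: "Summaries of PD measures will include both observed values and changes from timepoint-matched PD baseline values". SAP 9.1 follows this for the timepoint summaries. SAP 6.4.2 says: "If either the baseline or postbaseline value is missing, the change from baseline and percent change from baseline will also be missing". SAP 6.3.2 leaves the choice of baseline timepoints to Section 9, and Section 9 has no matching rule for an incomplete window.

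**The concern.** Under SAP 9.2 one surviving sample is enough to give a window value, so the missing-value rule in SAP 6.4.2 does not stop the calculation. A subject with both samples at baseline and only the 1000 h sample on Day 14 is assigned a change from the 0700/1000 h mean to a 1000 h value. Any difference between that subject's 0700 h and 1000 h levels is then counted as change on treatment. The same happens in mirror form when the baseline sample is the one lost.

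The outputs at stake are the window change and percent-change tables, the waterfall plots, the first responder definition and the PK/PD scatter plots. In a single-arm descriptive study of about 12 subjects, individual bars and points carry much of the PD message, so one distorted subject is visible.

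**Working it through.** **Inputs.** The window times and the single-sample rule come from SAP 9.2, the percent-change formula from SAP 6.4.2, the 50% cut from SAP 9.3, and the planned size of about 12 from SAP 4.1. The plan states no figure to reproduce. Two quantities are not in the documents: r = (1000 h value)/(0700 h value) within a subject, and the rate at which single samples are lost. I treat r as an assumption and show a range. Let f be the true ratio of Day 14 to baseline, taken as equal at both times.

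**Formulas.** In units of the baseline 0700 h value, the two-sample baseline is (1 + r)/2.
- Only 1000 h survives on Day 14: apparent ratio = f·r ÷ (1 + r)/2 = f·2r/(1 + r).
- Only 0700 h survives on Day 14: apparent ratio = f ÷ (1 + r)/2 = f·2/(1 + r).

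**No drug effect (f = 1), both baseline samples present.**

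| r | 1000 h only | 0700 h only |
|---|---|---|
| 1 | 0% | 0% |
| 0.8 | 1.6/1.8 = 0.889, -11% | 2/1.8 = 1.111, +11% |
| 0.7 | 1.4/1.7 = 0.824, -18% | 2/1.7 = 1.176, +18% |
| 0.5 | 1/1.5 = 0.667, -33% | 2/1.5 = 1.333, +33% |
| 1.25 | 2.5/2.25 = 1.111, +11% | 2/2.25 = 0.889, -11% |
| 2 | 4/3 = 1.333, +33% | 2/3 = 0.667, -33% |

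The signs reverse for r above 1.

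**Effect on the 50% cut.**
- r = 0.8, true reduction 45% (f = 0.55): 1000 h only gives 0.55 × 0.889 = 0.489, or -51%, a false responder. 0700 h only gives 0.55 × 1.111 = 0.611, or -39%.
- r = 0.5, true reduction 25% (f = 0.75): 1000 h only gives 0.75 × 0.667 = 0.50, or -50%, a false responder.
- r = 0.5, true reduction 50% (f = 0.5): 0700 h only gives 0.5 × 1.333 = 0.667, or -33%, a lost responder.
- A true 40% reduction becomes a responder on 1000 h alone when 1.2r/(1 + r) ≤ 0.5, that is r ≤ 0.714. A true 60% reduction is lost on 0700 h alone when 0.8/(1 + r) > 0.5, that is r < 0.6.

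**Sample lost at baseline instead.** With r = 0.5 and a true 40% reduction, the Day 14 mean is 0.6 × 0.75 = 0.45. Against baseline 0700 h alone (1) this reads -55%. Against baseline 1000 h alone (0.5) it reads -10%.

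**Size in the table.** One subject of 12 is 1/12 = 8.3 percentage points.

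**Matched rule.** Assume baseline values of 1200 and 600, a true 40% reduction and only 1000 h surviving on Day 14. The SAP rule gives 360/900, or -60%. Matching gives 360/600, or -40%, the same as the two-sample result. When the proportional effect is equal at both times, matching recovers it for every r.

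**BLQ route.** SAP 6.4.3 sets a BLQ value lying between two quantifiable values to missing. Assume baseline 1000/1000, Day 14 0700 h BLQ, Day 14 1000 h = 600, and an LLQ of 10 to 100. Setting BLQ to LLQ gives (10 + 600)/2 = 305 to (100 + 600)/2 = 350 against 1000, or -69.5% to -65%. Dropping the sample gives -40%, with or without matching.

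**The case against.** The strongest case on the other side is that this is an edge case under a rule fixed in advance. Harm needs one of two samples lost at one visit with no matching loss at the other, and a changed responder call also needs a subject near enough to the cut. The morning draws at baseline, Day 2 and Day 15 all fall within inpatient stays. Protocol 12.3 favours using whatever data exist. The study is descriptive, so no test, alpha or power is affected. All of that stands and limits the weight of the point. But using available data does not require comparing unlike clock times.

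Four stronger readings are tempting, and the documents do not support them.
- A reader might infer that the SAP abandons the protocol's matched change. SAP 9.1 delivers it for every parameter and timepoint, and the second responder definition, if read as same-time, also escapes. The gap is confined to the window change and what is built on it.
- A reader might infer that 0700 h and 1000 h levels differ sharply because both draws precede the delayed steroid dose. That timing shows neither a difference nor a flat profile, and SAP 9.2 treats the whole interval as the peak. The larger distortions above belong to assumed values of r.
- A reader might count the A4/T responder among the distorted changes. It uses observed window values at each visit against a fixed threshold. Both analytes are serum measurements from the same scheduled draws, so a missed draw removes both. Dividing across clock times needs the loss of one analyte only.
- A reader might take the distortion to be unrelated to the drug. Under SAP 6.4.3 a suppressed value can itself become missing, so loss may depend on response.

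**Conclusion.** The point holds as a gap in the change calculation. SAP 9.2 permits, and SAP 6.4.2 then computes, an unmatched window change whenever a morning sample is missing at only one of the two visits compared. Its direction depends on which sample survives and on whether r is below or above 1. With both baseline samples present and no drug effect, the spurious change runs from nothing at r = 1 to a third of baseline at r = 0.5 or r = 2. These sizes rest on assumed r and on an equal proportional effect at both times. The loss rate is unknown, and with no one-visit loss no result changes. It is worth correcting because the correction is cheap, not because the documents show the PD results to be at serious risk.

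**What to change.** In SAP 9.2 to 9.4:
- Compute change, percent change and the first responder definition from the morning timepoints present at both PD baseline and the postdose visit. Use the mean of two where both are shared and the single shared clock time otherwise. Set the change to missing if none is shared.
- Keep the current rule for observed-value summaries, with a footnote that the displayed change may differ from displayed postdose minus displayed baseline.
- Report how many window values at each visit rest on one sample.
- For A4/T, use only timepoints where both analytes are available.

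Matching does not cure missingness caused by the BLQ rule in SAP 6.4.3. That needs its own decision.

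The cost is a few sentences and a small programming change. A subject with no shared clock time drops out of the change summaries, and the Day 1 and Day 14 changes for one subject may use different baseline timepoints. With only one shared timepoint, the two responder definitions coincide for that subject.

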9.3. Responder Summaries

The PD biomarker data will also be summarized based on responder definitions for ACTH, 17-OHP, androstenedione, and testosterone (female subjects only). The first responder definition will be composed of subjects who have a 50% or greater reduction from PD baseline to Day 14 in the average of their morning window values. The second responder definition will be composed of subjects who have a 50% or greater reduction from PD baseline to Day 14 for at least one timepoint in the morning window period. The frequency and percentage of subjects meeting each of these responder definitions will be summarized by parameter.

Additionally, a responder definition for the ratio of androstenedione to testosterone (A4/T) in male subjects will be composed of male subjects who have an A4/T ratio greater than or equal to 0.5 (based on the average of the morning window values for androstenedione and testosterone) at PD baseline and who achieve an A4/T ratio less than 0.5 (based on the average of the morning

Neurocrine Biosciences, Inc. Statistical Analysis Plan

window values for androstenedione and testosterone) at Day 14. The frequency and percentage of male subjects meeting this responder definition will be summarized.

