9. PHARMACODYNAMIC DATA

PD biomarker data include measurements of ACTH, 17-OHP, androstenedione, testosterone, and cortisol. Note that all summaries of testosterone will be stratified by sex. The following sections describe the summaries and analyses of the PD biomarker data.

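### The male A4/T ratio is analysed only as a crossing of 0.5, so the size of its change is never estimated

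*SAP*

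**What the plan says.** SAP 9 defines the PD data: "PD biomarker data include measurements of ACTH, 17-OHP, androstenedione, testosterone, and cortisol". It adds: "Note that all summaries of testosterone will be stratified by sex". The A4/T ratio is not on that list.

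The listed hormones are then summarised continuously. SAP 9.1 gives observed values, time-matched change, 24-hour averages and individual curves. SAP 9.2 covers the 12- and 15-hour morning window for all of them except cortisol: "The morning window values will be summarized with descriptive statistics by PD parameter and visit", with change "as well as the percent change from PD baseline to Day 1 and from PD baseline to Day 14". Each person's percent change "for each subject will be presented as waterfall plots by PD parameter".

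SAP 9.3 adds responder counts. The two 50%-reduction rules apply to ACTH, 17-OHP and androstenedione in everyone, and to testosterone in females only. For males the section then defines an A4/T responder: "male subjects who have an A4/T ratio greater than or equal to 0.5" at PD baseline and "who achieve an A4/T ratio less than 0.5" at Day 14, both from morning-window averages. The only output named is that "The frequency and percentage of male subjects meeting this responder definition will be summarized".

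**The concern.** The SAP leaves male testosterone out of the 50% rules and gives males the A4/T ratio as their own responder measure. Every other responder parameter has a count and, beside it, change and percent change. The ratio has the count alone.

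A count of crossings says little about the size of an effect. It requires no minimum change, it depends on how far each male starts from 0.5, and it can register a large fall as a failure and a trivial one as a success. One of the three study objectives is to evaluate the effect of repeated dosing on PD biomarkers. In a study whose results are all descriptive summaries, a summary that omits the size of change leaves that part of the objective unanswered for this measure.

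**Working it through.** The plan states no figure for this measure, so there is none to reproduce. The check sets the sections side by side and then applies the rule.

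**1. Coverage by parameter (SAP 9 to 9.3)**

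| Parameter | Change from PD baseline | Morning-window percent change and waterfall | Responder count | Split by sex |
|---|---|---|---|---|
| ACTH, 17-OHP, androstenedione | yes | yes | 50% rules, both sexes | no |
| Testosterone | yes | yes | 50% rules, females only | yes |
| Cortisol | yes (9.1 only) | no | none | no |
| A4/T in males | no | no | crossing 0.5 only | males only |

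The PK/PD plots in SAP 9.4 do not include the ratio either.

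**2. The rule applied.** Responder means baseline >= 0.5 and Day 14 < 0.5. Percent change follows SAP 6.4.2: (Day 14 - baseline) / baseline x 100. The ratios are illustrative.

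| Baseline | Day 14 | Change | Percent change | Responder? |
|---|---|---|---|---|
| 3.0 | 0.6 | -2.4 | -80.0% | no |
| 3.0 | 0.50 | -2.5 | -83.3% | no |
| 0.52 | 0.48 | -0.04 | -7.7% | yes |
| 0.50 | 0.499 | -0.001 | -0.2% | yes |
| 0.45 | 0.10 | -0.35 | -77.8% | no (cannot qualify) |

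**3. Can the change in the ratio be recovered from the planned summaries?** For one male with percent changes pA in androstenedione and pT in testosterone, the Day 14 ratio divided by the baseline ratio is (1 + pA/100) / (1 + pT/100). This needs both values from the same male. The average of this quantity over males is not a function of average pA and average pT. The planned average pA also mixes males and females. The summary tables therefore cannot give it.

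**4. Precision of the count.** The planned size is about 12 across both sexes, and the number of males is not fixed. Assuming 4 to 8 males, one male moves the percentage by 1/4 = 25 points down to 1/8 = 12.5 points. Exact (Clopper-Pearson) 95% intervals when half respond:

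- 2/4: 6.8% to 93.2%
- 3/6: 11.8% to 88.2%
- 4/8: 15.7% to 84.3%

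**5. Crossing by chance (illustration only).** Let s be the within-subject SD of log(A4/T) between visits, and assume no drug effect. A male with measured baseline b is then below 0.5 at Day 14 with probability Phi( ln(0.5/b) / (s x sqrt 2) ). The documents give no s; 0.2 to 0.4 is assumed.

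| b | s = 0.2 | s = 0.3 | s = 0.4 |
|---|---|---|---|
| 0.55 | 0.368 | 0.411 | 0.433 |
| 0.80 | 0.048 | 0.134 | 0.203 |

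**6. Denominator.** SAP 9.3 does not say whether the percentage is of all males or of males with baseline >= 0.5. With 3 responders among 6 males, 4 of whom start at or above 0.5 (assumed), the result is 3/6 = 50% or 3/4 = 75%.

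**The case against.** The strongest reply is that the count does not stand alone. Both components of the ratio are summarised continuously in data that include males: testosterone separately by sex, androstenedione pooled. Males also count in the 50% rules for ACTH, 17-OHP and androstenedione. A large fall in A4/T has to come from lower androstenedione, higher testosterone, or both, and these would show in the individual curves and waterfall plots. This stands, and it rules out a stronger reading that a reader might infer: that the effect in males is never estimated, or that males have no other androgen result. The documents do not support either statement.

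Second, any cut-off rule produces pairs like those in the table. A rule that asks whether a male ends below 0.5 answers that question correctly. Neither document explains the choice of 0.5, so nothing here shows that it is unsuitable. That also stands. The point is the missing companion summary, not the threshold.

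Third, the chance-crossing rates rest on an assumed SD and chosen baselines, and no document shows that any male will start near 0.5. Coarse percentages affect every small subgroup in this study. Both are fair, so steps 4 and 5 are illustrations and not the basis of the finding.

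Fourth, the study is single-arm and descriptive, with no hypothesis test or power calculation. Nothing makes A4/T primary, and SAP 6 allows labelled post hoc analyses. This limits the importance of the point but does not remove it. Adding the summary before database lock keeps it among the pre-specified results, whereas adding it later makes it exploratory under the SAP's own terms.

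The objection does not show that the change in the ratio is reported anywhere. The individual displays show the two hormones separately, and a reader would have to match subjects across plots to rebuild the ratio.

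**Conclusion.** The point holds in this form: as written, the plan never estimates the size of change in the male A4/T ratio, and androstenedione, one of its components, is not summarised separately for males. This follows from the text of SAP 9 to 9.3 and needs no assumption. The rule's behaviour follows by arithmetic: an 80% fall can be a non-response, a 7.7% fall a response, and a baseline below 0.5 excludes response.

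The number of males (4 to 8), the within-subject SD (0.2 to 0.4) and the denominator example are assumptions. They show how little the count can carry and do not predict this trial's result.

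The practical weight is modest. No conclusion about safety, PK or the other biomarkers changes. The revision is worth making because it costs almost nothing and tells the reader more about the measure the SAP chose for males.

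**What to change.** 1. In SAP 9.2, add A4/T in males as a derived morning-window parameter, computed as in SAP 9.3 from the morning-window averages of androstenedione and testosterone. Report observed values at PD baseline, Day 1 and Day 14, with change and percent change (or the ratio of Day 14 to baseline).
2. Add an individual waterfall or paired plot. On a paired plot of observed ratios, draw a line at 0.5 so that crossing and size of change are seen together.
3. In SAP 9.3, keep the crossing count as a supplementary line. Use males with baseline A4/T >= 0.5 as the denominator, give the all-male count beside it, and show each male's baseline ratio.
4. If chance-crossing rates are quoted in the report, label them as illustrations under an assumed within-subject SD.

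The cost is one derived variable passed through table and plot programs that SAP 9.2 already requires. No new samples, visits or subjects are needed.

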9.4. Pharmacodynamic/Pharmacokinetic Relationship

The relationship between pharmacodynamic and pharmacokinetic data will be depicted graphically. Scatter plots of percent change from PD baseline to Day 14 in the average of morning window values vs. crinecerfont AUC_{0-12} will be generated for ACTH, 17-OHP, and androstenedione. These plots will also be generated for C_{max} .

10. PHARMACOKINETIC DATA

10.1. Plasma Concentrations

[figure not shown]
Plasma concentrations of crinecerfont and its metabolite, NBI-756179, will be summarized by visit, and nominal (scheduled) timepoint with descriptive statistics, which will include the coefficient of variation (CV [%]), geometric mean, and geometric CV (%). Figures of arithmetic mean (+SD) concentration vs. time curves will be generated by visit (Day 1, Day 14, and Day 14 through Day 35), and timepoint on both the linear and log (base10) scales.

In addition, these data will be displayed as individual subject plasma concentration vs. time curves by visit on both the linear and log (base 10) scales. Actual times from dosing rather than nominal timepoints will be displayed in the by-subject graphs.

All BLQ values (crinecerfont < 5.00 ng/mL; NBI-756179 < 0.500 ng/mL) will be set equal to zero (0) in the plasma concentration summaries, with the exception of the geometric mean and geometric CV (%) which will be treated as missing.

Subjects with significant deviations that could impact the interpretation of study data (eg, missed study drug dosing, emesis) will be excluded from summaries.

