Subjects will be admitted to the study center on Days 1 and 14 (first and last day of dosing). Subjects will have a blood sample collected on Day 1 for the first dose of study drug. The first dose of study drug, NBI-74788 50 mg, will be administered at approximately 1900 hours with subjects' evening meal on Day 1. Study drug will be administered at the study center on Days 2 and 14 with subjects' breakfast and evening meals, respectively. The subjects' usual morning dose of concurrent steroidal treatments, study drug dosing, and breakfast (snacks will be allowed prior to breakfast) will be delayed until after the 15-hour postdose PD samples are collected (ie, at approximately 1000 hours) on Day 2. The subjects' usual morning dose of concurrent steroidal treatments will be administered after the 15-hour postdose PD samples are collected (ie, at approximately 1000 hours) on Day 15. Subjects will be discharged from the study center in the evening on Days 2 and 15 following completion of all study-related procedures for those days. Study drug will be self-administered at home under parent/guardian supervision at approximately 0700 hours (with breakfast) and 1900 hours (with evening meal) on Days 3 to 13.

On Day 7 during the treatment period, PK, PD, and safety assessments will be conducted in an outpatient setting at the study center.

Follow-up visits on Days 17 and 21 will be conducted at the study center or by a qualified home healthcare provider at the subject's home (based on the subject's preference). A final study visit will be conducted at the study center approximately 3 weeks after the last dose of study drug (on Day 35 or early termination). There will be a visit window of -8 hours for Day 7, -8 hours/+3 days for Days 17 and 21, and +7 days for the final study visit (Day 35 or early termination). Safety, tolerability, PK, and PD will be assessed at scheduled times throughout the study.

Study Population: Approximately 12 pediatric female and male subjects (14 to 17 years of age) with a documented medical diagnosis of classic 21-hydroxylase deficiency CAH, who meet all protocol eligibility criteria, will be enrolled.

Duration of treatment: The expected duration of study participation for each subject is approximately 9 weeks, including up to approximately 3 weeks for screening, a 24-hour PD baseline period (approximately 7 days prior to the first day of dosing), 14 days of dosing, and a follow-up period of approximately 3 weeks.

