12.1. Analysis Sets

Data summaries for this study will be based on the safety analysis set, which will include all subjects who receive a dose of study drug. Additional analysis sets may be specified in the SAP.

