12.2. Sample Size

The sample size for this study is based on practical clinical considerations with no formal statistical power calculations.

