12.3. Handling of Missing Data

All available study data will be included in relevant summaries and data displays, including any available data for subjects with incomplete or missing data.

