6.2. Analysis Sets

6.2.1. Definition of Analysis Sets

6.2.1.1. Safety Analysis Set

The safety analysis set will include all subjects who take at least one dose of study drug and have any postbaseline safety data. The safety analysis set will be used for all summaries of safety data (e.g., AEs, clinical laboratory data) and pharmacokinetic data.

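### SAP 10.1 excludes whole subjects, not affected profiles, from plasma concentration summaries, so a missed home dose can also remove a valid Day 1–2 profile

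*SAP*

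**What the plan says.** SAP 10.1 (Plasma Concentrations) plans descriptive summaries of the drug and its metabolite by visit and scheduled timepoint, plus individual concentration curves. It ends with the exclusion rule: "Subjects with significant deviations that could impact the interpretation of study data (eg, missed study drug dosing, emesis) will be excluded from summaries". The rule does not define a significant deviation. It names no decision-maker and does not tie the exclusion to a profile, visit or sample.

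Other text bears on the same summaries:

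- SAP 6.2.1.1 says the safety analysis set "will be used for all summaries of safety data (e.g., AEs, clinical laboratory data) and pharmacokinetic data". Membership needs at least one dose and some postbaseline safety data. Table 2 assigns plasma concentrations and PK parameters to this set.
- SAP 6.2.2 counts exclusions and their reasons, but only for the defined analysis sets.
- Protocol 12.1 says: "Data summaries for this study will be based on the safety analysis set, which will include all subjects who receive a dose of study drug". It adds: "Additional analysis sets may be specified in the SAP". SAP 6.2 defines a pharmacodynamic set but no PK set.
- Protocol 12.3, on missing data, says: "All available study data will be included in relevant summaries and data displays, including any available data for subjects with incomplete or missing data".
- The visible text of SAP 10.2 (PK parameters) covers values below the quantitation limit and does not repeat the exclusion. SAP 9.4 plots PD change against AUC and Cmax and does not mention it either.

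**The concern.** Each subject contributes two PK profiles, Day 1–2 and Day 14–15. They answer different questions: exposure after the first dose and exposure at steady state. A deviation that spoils one need not touch the other. A dose missed at home cannot change concentrations measured before home dosing began, yet a rule written for subjects removes both profiles.

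Three things are at stake:

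- Valid first-dose data could be dropped from a study of about 12 subjects, and the subjects left in the summaries would be selected partly on adherence.
- Subjects removed under 10.1 remain in the safety set, so the table required by SAP 6.2.2 would not show that they were removed.
- Because the reach of the sentence is not stated, two programmers could build different tables from it. If it stops at concentrations, the concentration and parameter tables rest on different subjects. If it extends to AUC and Cmax, the PK/PD plots lose subjects who stay in the PD summaries.

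**Working it through.** **Inputs from the documents**

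- About 12 subjects, single arm. On the basis for this number the protocol says: "The sample size for this study is based on practical clinical considerations with no formal statistical power calculations". There is no power calculation to reproduce.
- PK sampling (Protocol 8.3): 4 samples on Day 1, 2 on Day 2, 1 on Day 7, 4 on Day 14, 3 on Day 15, and 1 each on Days 17, 21 and 35.
- Home dosing (Protocol 6): twice daily on Days 3 to 13, so 11 × 2 = 22 doses.

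**Input that is assumed.** The documents give no missed-dose rate. I take a per-dose probability p of 1, 2 or 5%, independent between doses.

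**Step 1: reproduce the plan's sample count.** 4 + 2 + 1 + 4 + 3 + 1 + 1 + 1 = 17, which matches the 17 PK samples in Protocol Table 3.

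**Step 2: what a home-dose miss cannot affect.** The Day 1–2 profile has 4 + 2 = 6 samples, and 6/17 = 35%. The last is at 12 hours, about 0700 on Day 2, before the delayed 1000 dose that day and before home dosing starts on Day 3. No miss on Days 3–13 can alter these six values.

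**Step 3: size under the strictest reading.** If any single missed home dose removes the subject, the chance of removal is 1 − (1 − p)^22, and the expected number removed is 12 times that.

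**Step 4: the same misses with exclusion by profile.** Day 1–2 loses nobody. For Day 14–15, suppose only the last four home doses count. That choice is purely illustrative, because the released documents give no half-life. The expected loss is 12 × [1 − (1 − p)^4].

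| p (assumed) | 1 − (1 − p)^22 | Subjects removed, of 12 (by subject) | Day 1–2 profiles lost (by profile) | Day 14–15 profiles lost (by profile, last 4 doses) |
|---|---|---|---|---|
| 1% | 0.198 | 2.4 | 0 | 0.5 |
| 2% | 0.359 | 4.3 | 0 | 0.9 |
| 5% | 0.676 | 8.1 | 0 | 2.2 |

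If the Day 14 morning dose in Protocol Table 1 is also taken at home, there are 23 home doses, and the by-subject column becomes 2.5, 4.5 and 8.3.

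**Step 5: effect on precision.** With the SD unchanged, the standard error grows by √(12/n). For n = 9 this is √(12/9) = 1.155, a 15% rise, and the half-width of a t-based 95% interval goes from 0.64 to 0.77 SD. For n = 6 it is √(12/6) = 1.414, a 41% rise, with a half-width of 1.05 SD.

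**The case against.** The strongest reply is that the rule is narrower than it looks. The deviation must be significant and must be capable of affecting interpretation. Missed dosing and emesis are examples, not automatic triggers. A Day 5 miss cannot affect Day 1–2 data, so a sensible analyst would not apply the rule there. Section 10.1 already summarises by visit and timepoint, so applying the exclusion by visit is a natural reading. This is plausible, and it makes the table's by-subject column an upper bound. It does not settle the matter, because the sentence removes subjects and does not limit the removal to a visit.

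A reader might infer that the rule breaches the protocol's commitment to use all available data. The documents do not support that. Protocol 12.3 concerns missing data and is limited to relevant summaries, and Protocol 12.1 lets the SAP add analysis sets. SAP section 12, where departures from the protocol would be declared, shows no text in this copy, so nothing can be said about disclosure. What stands is that 10.1 and 6.2.1.1 are not reconciled. A cross-reference could make the two work together.

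A reader might also infer that many valid profiles will be lost. No figure in the documents supports this. Home dosing is supervised by a parent or guardian, with a diary, a reminder call and capsule counts. Individual curves remain planned, so the values do not disappear from the report.

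Finally, a reader might suspect exclusions chosen after seeing the results. SAP section 2 puts analysis decisions before database lock, and SAP 8.2 has a committee review important deviations before lock. Section 10.1 does not refer to that process, and being before lock is not the same as being before the PK results are seen. Still, the documents give no ground for alleging selective exclusion, and the study is descriptive with no comparison between arms.

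**Conclusion.** The point holds as a defect in the unit and scope of the exclusion. Followed as written, a subject excluded for a missed home dose loses six Day 1–2 samples that the miss cannot have affected. The rule does not match the analysis set the SAP assigns to PK, and its reach beyond plasma concentrations is not stated.

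The size is uncertain. It runs from no subjects, if no deviation is judged significant, up to about 2, 4 or 8 of 12 at assumed independent per-dose miss rates of 1, 2 or 5%. Those upper figures also require every miss to trigger exclusion, which the text does not say. That six of 17 samples are at risk for each excluded subject follows from the sampling schedule and needs no assumed miss rate.

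**What to change.** Reword SAP 10.1 along these lines:

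- Exclude only the concentrations, and any parameters derived from them, of the profile that the deviation affects (Day 1–2 or Day 14–15). A deviation after the Day 1–2 samples never removes that profile.
- Fix in advance the interval before Day 14 within which a missed dose counts against the Day 14–15 profile. The sponsor should set it from its own PK knowledge, since the released documents give no half-life. State also how the rule treats the single Day 7 sample and the follow-up samples.
- Decide and record each exclusion, with its reason, before PK results are reviewed.
- List all excluded values, and show the summaries on all available data alongside.
- Cross-refer 6.2.1.1, 9.4, 10.1 and 10.2, so that the population behind the concentrations, parameters and PK/PD plots is explicit.

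The cost is SAP wording and one repeat table. No new data are needed.
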